12. RANDOMIZATION

Describe criteria for assigning subjects to sub-groups such as "control" and "experimental."

Although the participants among whom outcomes will be assessed are students, parents of these students will be the ones randomized to the treatment or control version of the app. A verification form on the informational FITSTART+ landing page, will serve two important purposes: (1) it will match parents to their students in the dataset; and (2) randomize parents to the treatment or control version of the app. The randomizer will be set up in Qualtrics to balance assignment to an app condition by students' birth sex. At the end of the verification form, parents will receive a web URL linking to the sign-up page for the application to which they were randomized. The treatment condition will receive the FITSTART+ intervention while the control group will receive a similar program which covers all non-alcohol related resources included in the intervention version of FITSTART+ (e.g., general parenting information, university-specific resources).

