Think of the occasion you drank the most in the **past 30 days**. How many **hours** did you spend drinking on that occasion?

During the **past 30 days**, how many times did you have [four/give] or more drinks within a 2 hour period?

▼ 0 occasions (0) ... 7+ occasions (7)

During the **past 30 days**, how many times did you have [eight/ten] or more drinks within a 2 hour period?

▼ 0 occasions (0) ... 7+ occasions (7)

Note: The BYAACQ was used in place of the RAPI to measure alcohol consequences.

Below is a list of things that sometimes happen to people either during or after they have been drinking alcohol. Next to each item below, please indicate whether that item describes something that has happened to you in the **past 30 days**.

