PRS Cover Page for Statistical Analysis Plan

Title: Parent Feedback Intervention Targeting Student Transitions and Alcohol Related Trajectories (+) Efficacy Study (FITSTART+)

Date: April 26, 2021

ClinicalTrials.gov Identifier: NCT04549454

Statistical Analysis Plan

Examines the efficacy of FITSTART+. Main effects of the intervention will be examined with hierarchical generalized linear models (HGLM) using SAS. HGLM permits the simultaneous examination of relationships among variables at different levels, for example variables measured over assessment periods assumed to fluctuate within an individual (e.g., student drinking behavior) with variables considered to have stable characteristics (i.e., parent intervention condition). Using this framework, time will be specified as a Level 1 varying predictor nested within individuals (Level 2). The following model will be used to determine main effects of the intervention conditions compared to control:

$$\text{Level 1: } DV_{ti} = \pi_{0i} + \pi_{1i}(T1)_{ti} + \pi_{2i}(T2)_{ti} + \varepsilon_{ti}$$

$$\text{Level 2: } \pi_{0i} = \beta_{00} + \beta_{01}(Tx)_i + r_{00i}$$

$$\pi_{1i} = \beta_{10} + \beta_{11}(Tx) \quad t \text{ indexes repeated measure} \quad \pi_{2i} = \beta_{20} + \beta_{21}(Tx) \quad i \text{ indexes individuals}$$

Respective model DVs will include total drinks per week from the DDQ, consequence composite score, and number of HED episodes during the past month. T1 and T2 will be dummy coded time variables (T1 = student baseline [coded 0] to 1 month into college follow-up [coded 1], T2 = student baseline [coded 0] to 6 months into college follow-up [coded 1]). Tx will be a categorical predictor comparing the intervention condition [coded 1] to control [coded 0]. With this model, intercept treatment differences will represent treatment differences at baseline (e.g., group differences in student drinking at baseline) and slope differences will represent changes over time (e.g., did students of intervention parents reduce their drinking between baseline and follow-up assessments more than students of control parents?). The intercept includes a random effect, which will model the subject-specific heterogeneity in the outcome and control for correlated data due to individuals. Pairwise comparisons (post hoc Tukey's) were conducted to examine mean differences between conditions at each time point.

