Missing data. Attrition bias will be tested by evaluating whether baseline outcomes differ between student and parent dropouts versus completers. HGLM is optimal in that it allows for unbalanced data, giving heavier weights to participants with more non-missing values. HGLM also assumes that missing values are missing at random as opposed to non-ignorable. The pattern-mixture approach to non-ignorable missing data will be used to assess the sensitivity of findings to the presence of missing data. If the pattern of missingness appears to pose a threat to the validity of the experimental manipulation (i.e., student attrition is related to parent random assignment, or the predictors of attrition are different for students of intervention vs control parents), more powerful missing techniques will be used, such as multiple imputation.

Additional Model Considerations. Student outcomes (drinks per week, HED frequency, and negative consequences) are count variables, which can have skewed distributions when the overall mean is low. Alternative models could also specify a Poisson or Gaussian distribution for the Level 1 errors. We will consider whether the

Level 1 components are more appropriately modeled as Gaussian or Poisson. Further, in spite of randomization at the parent level, we will conduct baseline equivalence tests between the FITSTART+ student participants to establish successful parent randomization effectiveness, including pre-treatment alcohol use, negative consequences, and demographic variables. Any student variables that are associated with treatment assignment, in spite of parent randomization, will be included as covariates.

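### Assignment is balanced on students' birth sex, but the outcome model has no birth-sex term and the covariate rule will almost never admit one; the cost is small and falls mainly on the time-point comparisons.

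*Protocol*

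**What the plan says.** Protocol section 12 (and, in the same terms, section 3) names a single balancing factor: "The randomizer will be set up in Qualtrics to balance assignment to an app condition by" students' birth sex. Birth sex is also a survey item in the Measures Appendix.

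The SAP fits one model to three outcomes: "Respective model DVs will include total drinks per week from the DDQ, consequence composite score, and number of HED episodes during the past month". Level 1 has two time dummies. At Level 2 the intercept and both time slopes depend on treatment arm only, and the intercept also has a random effect. Birth sex appears at neither level. The treatment effect is read from the slope differences, and post hoc Tukey comparisons of the arms at each time point are added.

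Under Additional Model Considerations the SAP runs baseline equivalence tests, "including pre-treatment alcohol use, negative consequences, and demographic variables". It then gives its only route to a covariate: "Any student variables that are associated with treatment assignment, in spite of parent randomization, will be included as covariates". No test or significance level is stated for that association. Neither document commits to a sex term, a sex-by-time term or a sex-stratified analysis.

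**The concern.** A factor is normally balanced in the allocation because it is expected to matter for the outcome, and the analysis should then condition on it. Here the covariate rule works the other way. Sex is a demographic variable and so is formally eligible, but the rule waits for an association with assignment that the randomizer is set up to prevent.

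Balancing removes the chance difference between arms that is due to sex. A model without sex still counts the spread between the sexes as error. The reported standard error of an arm difference at a time point is then larger than its true sampling error, and the test is conservative. At stake is some precision that the design has already provided, together with the prespecified status of the adjustment: if sex were added later, outside a rule that does not call for it, the change would look post hoc.

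**Working it through.** The plan gives no figure for the influence of sex, so there is none to reproduce. The nearest is the SAP's power statement (300 per arm, 20% attrition, d = 0.20 and 0.40), which calls the power excellent but gives no number, alpha or within-person correlation.

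**Assumptions, none from the documents:** two-sided alpha 0.05 with no multiplicity adjustment; 60% female (p = 0.6); sex difference δ in within-sex SD units; Gaussian outcome; near-exact balance; within-person correlation 0.6 for change contrasts.

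**Step 1. Will the rule admit sex?** This was simulated with 20,000 runs, 600 students and a chi-square test at 0.05.

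| Assignment | No attrition | 20% random attrition | 50% random attrition |
|---|---|---|---|
| Simple randomization | 4.8% | 5.0% | 5.0% |
| Balanced on sex | 0.0% | 0.0% | 0.6% |

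**Step 2. One time point, no sex term.** Let v = p(1 − p)δ² = 0.24δ². Then R² = v/(1 + v), the SE ratio is 1/√(1 − R²) = √(1 + v), and the actual type I error is 2[1 − Φ(1.96√(1 + v))].

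| δ | v | R² | SE ratio | Type I error |
|---|---|---|---|---|
| 0.2 | 0.0096 | 1.0% | 1.005 | 4.9% |
| 0.4 | 0.0384 | 3.7% | 1.019 | 4.6% |
| 0.6 | 0.0864 | 8.0% | 1.042 | 4.1% |

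**Step 3. Power at one time point, d = 0.20.** With 20% attrition, 300 × 0.8 = 240 students per arm remain. With sex in the model, power is Φ(0.20√(240/2) − 1.96) = Φ(2.191 − 1.96) = 59%. Without it, 1.96 is replaced by 1.96√(1 + v). The simulation used 4,000 runs.

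| δ | Power without sex, formula | Power without / with sex, simulated | Type I error without / with sex, simulated |
|---|---|---|---|
| 0.3 | Φ(2.191 − 1.981) = 58% | 60% / 61% | 4.5% / 4.7% |
| 0.5 | Φ(2.191 − 2.018) = 57% | 56% / 58% | 4.2% / 4.9% |
| 0.8 | Φ(2.191 − 2.105) = 53% | 53% / 59% | 3.1% / 4.8% |

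The simulated powers have a Monte Carlo error of about 0.8 points, so the three values with sex all estimate the same 59%.

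**Step 4. Treatment-by-time contrast.** A stable sex difference cancels from a within-student change, and the random intercept absorbs it. Simulated power is 69% to 70% with or without sex. The formula gives the same: the change SD is √(2(1 − 0.6)) = 0.894, and Φ(2.191/0.894 − 1.96) = 69%.

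If the sex difference starts at 0.5 SD and grows by a further 0.5 SD, simulated power is 64.8% without a sex-by-time term and 67.2% with one. As a check, the change variance becomes 0.8 + 0.24 × 0.25 = 0.86, and Φ(2.449 − 1.96√(0.86/0.8)) = 66% against 69%, a gap of similar size.

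**The case against.** The strongest reply is that the quantified loss does not fall on the main test. The SAP reads the intervention effect from the slopes, where a stable sex difference drops out. The time-point comparisons are post hoc. Even there the loss is about one to two power points for sex differences of 0.3 to 0.5 SD, and it takes 0.8 SD to lose about six. The error is in the conservative direction. All of this stands, and it sets the size of the point.

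The limits of the arithmetic also stand. The sex split and sex effects are assumed. The documents do not say how tightly the randomizer balances. The SAP describes the outcomes as counts for which a Poisson model may be used, and that case was not simulated.

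Three stronger readings are tempting, and the documents support none of them:

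- **Sex must predict heavy episodic drinking because its threshold is sex-specific.** The items ask "how many times did you have [four/give] or more drinks within a 2 hour period" (the second value is presumably five) and "how many times did you have [eight/ten] or more drinks within a 2 hour period". Sex is the likely switch, but the items do not say so. A lower cut-off for one sex can also narrow the sex difference in counts, so the wording is not evidence that sex predicts this outcome.
- **The adjustment saves students for the trial as a whole.** The v column in Step 2 could be read as 1%, 4% or 9% more students. It applies only to the reported precision of a time-point comparison.
- **The treatment effect is biased or false positives rise.** Neither follows from omitting a factor that is balanced between the arms.

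The reply does not rescue the covariate rule. Screening demographics does not cover birth sex when balancing has removed the trigger.

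**Conclusion.** The point holds as a modest efficiency and prespecification issue. The design balances on birth sex, the model omits it, and the rule for adding covariates will almost never bring it in.

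The post hoc arm comparisons at each time point are mildly conservative if sex predicts drinking, to the extent shown in Step 2 and under the assumptions listed there. The main treatment-by-time contrasts are essentially unaffected by a stable sex difference. They gain about two power points in the example where the difference grows by 0.5 SD, and the documents give no data on whether it does. The validity of the main result is not in question. The change is still worth making, because it uses a variable the trial already collects and balances on.

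**What to change.** In the SAP's model description, add student birth sex as a fixed Level 2 covariate on the intercept for all three outcomes, to be included whatever the baseline equivalence tests show. Under Additional Model Considerations, limit the association rule to variables other than birth sex.

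Sex-by-T1 and sex-by-T2 terms are optional. They help the slope contrasts only if the sex difference changes after students reach college, so the choice should be made and recorded before outcome data are seen. It would also help to state in the Measures Appendix which threshold each student is shown.

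The cost is a line or two of SAP text and one degree of freedom, or three with both interaction terms. No new data are needed.

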13. USE OF DECEPTION

If the project involves deception, describe the debriefing procedures that will be used.

Include, verbatim, the following statement in the consent form: "Some of the information with which I will be provided may be ambiguous or inaccurate. The investigator will, however, inform me of any inaccuracies following my participation in this study."

N/A

14. QUESTIONNAIRES AND SURVEYS

Include copies of questionnaires or survey instruments with the application (draft form is acceptable).

If not yet developed, please so indicate and provide the Committee with an outline of the general topics that will be covered. Also, when the questionnaire or interview schedule has been compiled, it must be submitted to the Committee for separate review and approval. These instruments must be submitted for approval prior to their use.

Consider your population. If they are foreign speakers, please include copies in the foreign language.

Please see attached MEASURES APPENDIX

15. PHYSICIAN INTERACTIONS

To ensure that all patients receive coordinated care, the principal investigator is obligated to inform the primary physician (when not the principal investigator) of all studies on his/her patients.

N/A

16. SUBJECT SAFETY

Describe provisions, if appropriate, to monitor the research data collected, to ensure continued safety to subjects.

High-risk drinking levels and the endorsement of high levels of negative consequences by students will be continually monitored during all phases of the study. Specifically, students reporting consumption of potentially lethal doses of alcohol (BAC's above .30) or RAPI consequences scores (incidence) of 16 or above on the initial or any follow-up questionnaire will be contacted and informed of their risk and provided referrals for clinical services. The research team will provide treatment referrals to participants who demonstrate significant increases in alcohol consumption in the follow-up phases compared to baseline assessment. See section 18 for more information about the referral process.

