The proposed study will evaluate the efficacy of a parent-based normative feedback intervention that aims to leverage parental influence to reduce the risk for heavy drinking and associated consequences among incoming first-year college students. Parents in the intervention group will learn about the risks of alcohol use among students and discuss strategies to maintain an open dialogue with their child regarding alcohol-related attitudes and expectations. It is anticipated that parents and students in the intervention condition will gain substantial benefit from participating in the study, with regard to parents learning about alcohol risk and communication, and students engaging in less risky alcohol use behaviors and negative alcohol-related consequences. In addition, all student participants in both the intervention and control groups will be monitored for high-risk drinking levels and endorsement of high levels of negative consequences, and will be provided appropriate referrals when necessary. Specifically, participants reporting consumption of potentially lethal doses of alcohol (BAC's above .30) or RAPI consequences scores (incidence) of 16 or above on the initial or any follow-up questionnaire will be contacted and informed of their risk, and provided referrals for clinical services. This is a benefit that would not otherwise occur without study participation.

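### The consequence-based referral trigger is a RAPI score of 16 or above, but the BYAACQ replaced the RAPI and the visible text gives no BYAACQ cut-off

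*Protocol*

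**What the plan says.** Protocol section 16 (Subject Safety) opens with a general commitment: "High-risk drinking levels and the endorsement of high levels of negative consequences by students will be continually monitored during all phases of the study". It then makes this operational with two numeric triggers. One is an estimated BAC above .30. The other concerns alcohol consequences: students with "RAPI consequences scores (incidence) of 16 or above on the initial or any follow-up questionnaire will be contacted and informed of their risk" and given referrals to clinical services. A third, non-numeric route follows, under which the team will provide "treatment referrals to participants who demonstrate significant increases in alcohol consumption in the follow-up phases compared to baseline assessment".

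Section 4 (Risks / Benefits) repeats both numeric triggers, again naming "RAPI consequences scores (incidence) of 16 or above on the initial or any follow-up questionnaire will be contacted". It presents the monitoring and referral, which cover both arms, to the IRB in these terms: "This is a benefit that would not otherwise occur without study participation".

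The Measures Appendix, just before the consequence items, states: "Note: The BYAACQ was used in place of the RAPI to measure alcohol consequences". The instruction to students under that note is to read a list of events and, for each, "please indicate whether that item describes something that has happened to you in the" past 30 days.

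**The concern.** The safety rule and the survey name different instruments. A threshold defined on the RAPI needs a RAPI score, and by the appendix's own statement the survey does not collect one. It looks as though the instrument was changed and the two sections that depend on it were not updated.

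At stake is the step that turns a commitment to watch for high levels of consequences into contact with a particular student. Participants are 17 to 20 years old and some are minors. Section 16 lists consequences separately from drinking levels, so the plan treats them as a distinct reason to act. The benefit described to the IRB in section 4 rests in part on this trigger.

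**Working it through.** No formula applies. The documents give no derivation of the value 16, and no BYAACQ scoring or item count from which an equivalent could be calculated. The check is to set the relevant texts side by side.

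1. **Where the trigger stands.** It appears in Protocol sections 4 and 16, with the same instrument and the same value (RAPI, *incidence*, 16 or above), at the initial and every follow-up questionnaire.
2. **What the survey collects.** According to the Measures Appendix, this is the BYAACQ in place of the RAPI, with each item asked as having happened or not in the past 30 days.
3. **Whether anything links the two.** The BYAACQ is named only in the appendix note. Nothing visible gives a BYAACQ threshold, a conversion, or a statement that 16 is retained.
4. **What still works.**
   - *BAC above .30.* The appendix collects birth sex, weight, maximum drinks on one occasion and hours spent drinking on the heaviest occasion, so this trigger appears workable.
   - *Increased consumption.* This needs a rise from baseline, so it can act only at the two follow-ups. It measures intake rather than harm.
   - *Adverse events.* Section 18 offers a counselling and assessment session to every student who reports an alcohol, drug or mental health AE or SAE, whether or not it is related to the study. It is not limited to serious events, but it does not say which survey answers count as an AE.

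   None of these three is a consequence-score criterion.
5. **Count.**

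| Item | Stated | Applicable as written |
|---|---|---|
| Numeric triggers (BAC, RAPI) | 2 | 1 |
| Consequence-score triggers | 1 | 0 |
| Surveys at which the RAPI trigger should act (baseline + 2 follow-ups) | 3 | 0 |

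Followed literally, the rule flags no student on consequences at any of the three surveys. This count describes the wording. It does not estimate how many students are affected.

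**The case against.** The strongest reply is that staff could simply apply 16 to the new scale. The trigger is qualified as an *incidence* score, and the appendix asks whether each item happened. If *incidence* means the number of consequences endorsed, the two scores have the same form and the rule could be used in practice. This is a fair reading, and it is why the point is limited to the rule as written. It does not settle the matter. The term is not defined, the documents do not say that 16 carries over, and a threshold set for one list of items need not mean the same on another.

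A second reply is that other routes to help exist. That stands. A reader might infer that safety monitoring has failed or is missing, or that students with many non-serious consequences have no route to referral. The documents do not support either. The BAC and increased-consumption routes do not depend on the RAPI, and section 18 covers non-serious AEs. Because AEs are not tied to survey items, the gap that remains cannot be sized.

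A third reply is that a revised threshold may exist elsewhere. The form text in section 14 requires instruments to be submitted for approval before use, so a separate submission may have dealt with it, and the BYAACQ items themselves are not visible after the instruction. This cannot be excluded. The two sections that state the rule are visible, however, and both still name the RAPI.

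Finally, the note is in the past tense, so the surveys may be finished. In that case rewording protects no current participant, and late contact would have limited value because the answers cover only a 30-day window. What then remains useful is a record of the rule that was actually applied.

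**Conclusion.** The inconsistency is real and rests on direct statements in the current Protocol. The only consequence-score trigger cannot be applied as written at any of the three surveys, and it is one of the two numeric triggers. Safety monitoring is reduced, not absent.

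The conclusion rests on two assumptions: that the appendix note correctly describes the survey, and that no BYAACQ cut-off is set out in material not visible here. A reader might go further and infer that students were in fact missed. The documents give no score distribution and do not report which rule staff used, so the number of missed referrals is unknown and may be zero. Sample size, power and type I error are unaffected. The point should be corrected because it concerns participant safety and the correction is cheap.

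**What to change.** In Protocol sections 4 and 16, replace the RAPI trigger with one on the past-30-day BYAACQ score, applied at baseline and at each follow-up and approved by the IRB. Either of two forms would do:

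- a BYAACQ cut-off chosen and justified by the investigator; or
- an explicit statement, with its rationale, that the threshold is 16 endorsed BYAACQ items.

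The documents do not contain what is needed to choose the value, so none is proposed here. If the surveys have already been run, document which BYAACQ cut-off was used for referral.

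The cost is a wording amendment in two sections with IRB approval, and possibly some additional referrals. No new data collection is needed.
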